1.3.3 Safety Objectives

- To assess the safety and tolerability, including the incidence of adverse events (AEs) and
 events of hypoglycemia, of dapagliflozin and saxagliptin as add-on to diet and exercise and
 metformin (IR or XR), or insulin, or metformin (IR or XR) plus insulin in pediatric T2DM
 subjects when administered for up to 26 weeks of short-term (ST) double-blind treatment, and,
 separately, up to 52 weeks of total treatment.
- To assess the incidence of diabetic ketoacidosis (DKA) with dapagliflozin and saxagliptin as
 add-on to diet and exercise and metformin (IR or XR), or insulin, or metformin (IR or XR)
 plus insulin in pediatric T2DM subjects when administered for up to 26 weeks of ST doubleblind treatment, and, separately, up to 52 weeks of total treatment.
- To assess measures of growth and maturity and Tanner staging and markers of bone health in pediatric T2DM subjects when administered dapagliflozin or saxagliptin as add-on to diet and exercise and metformin (IR or XR), or insulin, or metformin (IR or XR) plus insulin for up to 26 weeks of ST double-blind treatment, and, separately, for up to 52 weeks of total treatment, and for an additional 52 weeks after the study has been completed and study-related treatment has been discontinued.
- To assess the safety and tolerability of dapagliflozin (or saxagliptin) monotherapy in pediatric subjects who are randomized to withdraw background metformin.

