| Pregnancy Test (WOCBP only) | X | | X | X | X | X | X | WOCBP must have a negative serum or urine pregnancy test within 24 hours prior to the start of study drug. Home pregnancy kits will be provided. |

Table 5.1-2: Short-term Procedural Outline (CV181375 [D1680C00019])

| Procedure | Day 1ª | Wk 2 ^{a,b} | Wk 6 ^a | Wk 12 ^a | Wk 14 ^{a,c} | Wk 20 ^a | Wk 26/ETD (early discontinuation of IP)/Rescue ^{a,c} | Notes |
|---|-----------|------------------------|----------------------|-----------------------|-------------------------|-----------------------|--|---|
| Spot Urine Glucose | X | | X | X | | X | Х | Results blinded to the Sponsor, Investigator, site, and subject for the duration of the study following IP administration on Day 1 until after study completion |
| Growth, bone and maturation markers | X | | | | | | X | Thyroid-stimulating hormone (TSH), free thyroxine, luteinizing hormone (LH), follicle-stimulating hormone (FSH), estradiol, total testosterone, insulin-like growth factor-1 (IGF-1), insulin-like growth factor binding protein-3 (IGFBP-3), calcitonin, 25-hydroxy vitamin D, bone alkaline phosphatase, osteocalcin, parathyroid hormone (PTH) and carboxyterminal cross-linked telopeptide of Type 1 collagen (CTX-1) |
| Plasma samples for analysis of dapagliflozin, saxagliptin and 5-OH-saxagliptin ^d | | | X | X | | X | X# | Samples will be collected pre-dose and approximately 2 hours post-dose (± 1 hour) Samples will be drawn in the fasting condition. # No samples will be drawn at the Rescue Visit or the Week 26 Visit following Early Treatment Discontinuation Visit |
| Plasma samples for DPP-4 activity ^d | х | | X | Х | | Х | X | On Day 1 plasma samples for DPP-4 activity will be drawn pre-dose only. At the Weeks 6, 12, 20 and 26 visits, plasma samples for DPP-4 activity will be drawn at 2 hours (± 1 hour) post-dose only. Samples will be drawn in the fasting condition. |

Table 5.1-2: Short-term Procedural Outline (CV181375 [D1680C00019])

| Procedure | Day 1 ^a | Wk 2 ^{a,b} | Wk 6 ^a | Wk 12 ^a | Wk 14 ^{a,c} | Wk 20 ^a | Wk 26/ETD (early discontinuation of IP)/Rescue ^{a,c} | Notes | | | |
|---|-----------------------|------------------------|----------------------|-----------------------|-------------------------|-----------------------|--|---|--|--|--|
| Study Drug / IXRS | | | | | | | | | | | |
| Contact IXRS | X | | X | | X | X | X | | | | |
| First randomization | X | | | | | | | | | | |

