- Eligible subjects who are receiving active treatment will be grouped into two separate strata for dapagliflozin and saxagliptin, and then randomised 1:1 within each strata to either discontinue background medication with metformin or to continue background medication with metformin. For subjects on active treatment who are randomised to withdraw background medication with metformin, those who are currently receiving high doses of saxagliptin (5 mg) or dapagliflozin (10 mg) will continue to receive the high doses, whereas subjects who are currently receiving low doses of saxagliptin (2.5 mg) or dapagliflozin (5 mg) will have their doses up-titrated to the high doses (saxagliptin 5 mg or dapagliflozin 10 mg). Subjects in the active treatment arms who are randomised to continue background medication with metformin will continue with their current dose of either saxagliptin or dapagliflozin.
- Eligible subjects who are receiving placebo will be randomised 1:1:1 to either withdraw background medication with metformin and switch to active treatment with either saxagliptin 5 mg or dapagliflozin 10 mg or to remain on background medication with metformin and continue with placebo.

[figure not shown]
The study design schematic for subjects not undergoing randomised withdrawal of background medication at Week 32 or Week 40 is presented in [Figure 2](#).

Figure 2 Study design schematic for subjects not undergoing randomised withdrawal of background medication at Week 32 or Week 40

The study design schematic for subjects undergoing randomised withdrawal of background medication at Week 32 or Week 40 is presented in [Figure 3](#).

[figure not shown]
Figure 3 Study design schematic for subjects undergoing randomised withdrawal of background medication at Week 32 or Week 40

*Subjects who fail to qualify at Week 26 due to HbA1c ≥ 7.5% at Week 26 may qualify at Week 32 if HbA1c < 7.5% at Week 32.

The subgroups following the third randomisation at Week 32 or Week 40 are presented in [Figure 4](#).

Figure 4 Subgroups following the third randomisation at Week 32 or Week 40

^a Subjects who fail to qualify for the third randomisation due to HbA1c ≥ 7.5% at Week 26 may qualify at Week 32 if HbA1c < 7.5% at Week 32.

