3.4.9 Measures of growth and maturity

Measures of growth and maturity include Tanner staging and central laboratory evaluations of growth and maturation markers and bone biomarkers. These will be assessed during the lead-in visit (Tanner staging only) or Day 1 prior to first dose (growth, bone and maturation markers only), and at Week 26, Week 52, Week 104, and (if applicable) at the ETD, Rescue and non-treatment follow-up visits.

Tanner staging is a measure of pubertal development rated on a scale of stage 1 to stage 5 (for details see Appendix Section 8.10.1). Tanner staging will be determined based on investigator assessment and the subjects' self-reports.

Growth and maturation markers

- Thyroid-stimulating hormone (TSH),
- Free thyroxine (assessed at Screening if TSH is abnormal),
- Luteinising hormone (LH) (females only),
- Follicle-stimulating hormone (FSH) (females only),
- Oestradiol (females only),
- Total testosterone (males only),
- Insulin-like growth factor-1 (IGF-1),
- Insulin-like growth factor binding protein-3 (IGFBP-3),
- Calcitonin,
- 25-hydroxy vitamin D.

Bone biomarkers

- Bone alkaline phosphatase,
- Osteocalcin,
- Parathyroid hormone (PTH),

- Carboxyterminal cross-linked telopeptide of Type 1 collagen (CTX-1).

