4.7 Safety

Safety analyses will be conducted for the ST, ST+LT, and randomised withdrawal (as applicable) periods. An additional safety analysis will be provided for the post-study visit at Week 104, to summarise assessments of measures of growth and maturity by treatment group. Summaries will be based on the Treated Subjects Data Set unless otherwise stated.

The primary analyses of safety will include data regardless of rescue medication initiation, unless otherwise specified. Additional sensitivity analyses on data collected prior to rescue will be performed for AEs and laboratory marked abnormalities.

Dapagliflozin and saxagliptin will be summarised separately. Both low-dose and high-dose dapagliflozin/saxagliptin groups will be combined for dapagliflozin/saxagliptin to provide the

safety summary for overall dapagliflozin/saxagliptin compared to placebo. A common placebo group will be included in each summary.

Additional analyses will be performed during the ST+LT period to account for the randomised withdrawal design:

- Safety analyses conducted during the ST+LT period will also be conducted during the treatment period up to Week 32.
- Safety analyses conducted during the ST+LT period will also be conducted based on the treatment received at the time of the assessment to account for changes in treatment during the randomised withdrawal period (dapagliflozin/saxagliptin/placebo).
- Weighted analysis will be conducted for select safety parameters including adverse events, marked abnormal labs and ECGs using the original randomised groups to assess the effects of dapagliflozin (or saxagliptin) versus placebo on safety endpoints for subjects on background medication (i.e., excluding subjects re-randomised to withdraw from metformin).

The weight matrix denoted by W_3 is defined as follows:

$$W_3 = \text{Diag} \begin{bmatrix} \mathbf{0}_{1 \times \frac{rn}{2}} \\ \mathbf{2}_{1 \times \frac{rn}{2}} \\ \mathbf{1}_{1 \times (1-r)n} \\ \mathbf{0}_{1 \times \frac{2rn}{3}} \\ \mathbf{3}_{1 \times \frac{rn}{3}} \\ \mathbf{1}_{1 \times (1-r)n} \end{bmatrix}$$

where r is the proportion of subjects eligible for the third randomisation and n is the number of subjects within an arm.

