W_3 : For the weighted analyses, dapagliflozin (or saxagliptin) subjects who went through the third randomisation and withdrew metformin will be assigned a weight of zero, and those randomised to stay on metformin will be assigned a weight of 2. All other dapagliflozin (or saxagliptin) subjects will be assigned a weight of 1. Placebo subjects randomised to withdraw metformin and switch to active treatment will be assigned a weight of 0. Placebo subjects randomised to stay on metformin will be assigned a weight of 3. All other placebo subjects will be assigned a weight of 1.

- Safety analyses will be conducted during the randomised withdrawal period using the Randomised Withdrawal Subjects Data Set.

For subjects initially randomised to the dapagliflozin (or saxagliptin) group, the subjects re-randomised to withdraw metformin will be compared to the subjects re-randomised to stay on metformin. Separate analyses will be performed for subjects respectively randomised to either dapagliflozin or saxagliptin group.

For subjects initially randomised to the placebo group, the subjects who were re-randomised to switch to dapagliflozin (or saxagliptin) monotherapy will be compared to the subjects who were re-randomised to stay on placebo with background metformin. Separate analyses will be performed respectively for subjects re-randomised to dapagliflozin and for those re-randomised to saxagliptin, using the those re-randomised to placebo as comparator.

Additional analyses (for AEs, hypoglycaemic events, and MA labs only) will also be performed to compare all subjects taking dapagliflozin (or saxagliptin) monotherapy versus those taking placebo with background metformin during the randomised withdrawal period (adding placebo subjects randomised to withdraw metformin and switched to dapagliflozin [or saxagliptin]) monotherapy to dapagliflozin (or saxagliptin) subjects randomised to withdraw metformin).

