4.7.7 Measures of growth and maturity

4.7.7.1 Tanner stages

Tanner stages will be summarised based on observed data, regardless of rescue medication initiation. Summaries of descriptive statistics will be provided for baseline, Week 26, Week 52, and for the post-study visit at Week 104 using the LOCF approach in the period. Changes from baseline at these time points will be provided using shift tables and by visit according to baseline status. Also, change from Week 26 status to Week 52 and change from Week 52 status to Week 104 according to baseline status will be presented. A weighted analysis, as described in Section 4.7, to account for the randomised withdrawal design may also be presented.

In addition, Tanner staging will also be summarised as above during the randomised withdrawal period, using the Randomised Withdrawal Subjects Data Set for the first two treatment comparisons described in Section 4.1.5. Summaries of descriptive statistics will be provided for withdrawal baseline, Week 52 and Week 104 using the LOCF approach. Changes from withdrawal baseline at Week 52 and Week 104 will be provided using shift tables, for Week 52 and Week 104 according to withdrawal baseline status and also for Week 104 according to Week 52 status.

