4.7.7.3 Growth and maturity markers

Summaries of growth and maturation markers (see Section 3.4.9) in SI and conventional units will be based on observed data, regardless of rescue medication initiation. Descriptive summaries of absolute values and changes from baseline (where applicable) will be provided for baseline, Week 26, Week 52, and for the post-study visit at Week 104 using the LOCF approach. For the Week 104 analyses, change from Week 52 will also be presented.

In addition, growth and maturation markers will also be summarised during the randomised withdrawal period using the Randomised Withdrawal Subjects Data Set for the first two treatment comparisons described in Section 4.1.5. Descriptive summaries of absolute values and changes from withdrawal baseline (where applicable) will be provided for withdrawal baseline, Week 52 and Week 104 using the LOCF approach.

A categorical change from baseline summary will also be produced by treatment group, age category (≥ 10 and < 15 years, ≥ 15 and < 18 years) using the randomisation strata, and puberty status at Week 26, Week 52 and Week 104 (as defined in Appendix Section 8.10.3) for Week 26, Week 52, and for the post-study visit at Week 104 using the LOCF approach. Similarly, a categorical change from withdrawal baseline summary will also be produced for the Randomised Withdrawal Subjects Data Set for Week 52 and Week 104 using the LOCF approach.

A listing of the growth and maturation markers along with the Tanner stages by subject will be provided. For the ST+LT period this listing will include all data collected up to the end of the LT period. For the ST+LT + Week 104 period, the listing will include all data collected up to Week 104.

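### No weighted Week 52 summary is specified for weight, height and BMI, growth and maturation markers or bone biomarkers, so their original-arm tables mix treatments after the third randomisation

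*SAP*

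**What the plan says.** **Objective.** Protocol 1.3.3 includes the aim "To assess measures of growth and maturity and Tanner staging and markers of bone health in pediatric T2DM subjects" given either drug as an add-on, over 26 weeks and separately over up to 52 weeks of treatment. Safety of monotherapy after metformin withdrawal is a separate objective in the same section.

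**Third randomisation.** SAP 1.2: "Eligible subjects who are receiving placebo will be randomised 1:1:1 to either withdraw background medication with metformin and switch to active treatment", with the third group staying on metformin and placebo. Eligible drug-arm children are split 1:1 between stopping and keeping metformin. Those who stop while on the low dose also move to the high dose.

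**How safety analyses allow for it.** SAP 4.7 adds three forms of the ST+LT (52-week) analyses: data up to Week 32, grouping by treatment received at the assessment, and W3 weights. On the last: "Weighted analysis will be conducted for select safety parameters including adverse events, marked abnormal labs and ECGs using the original randomised groups". For placebo, "Placebo subjects randomised to withdraw metformin and switch to active treatment will be assigned a weight of 0"; those kept on placebo and metformin get 3. In the drug arms the weights are 0 (metformin stopped) and 2 (metformin kept). Everyone not re-randomised gets 1.

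**The measures at issue.** For growth and maturation markers, SAP 4.7.7.3 states: "Descriptive summaries of absolute values and changes from baseline (where applicable) will be provided for baseline, Week 26, Week 52", plus Week 104. Section 4.7.7.4 does the same for bone biomarkers, and 4.7.6 covers weight, height and BMI by visit. Each adds a summary in the Randomised Withdrawal Subjects Data Set. None mentions weights, and Table 24 lists no weighted entry for them. For Tanner stage, 4.7.7.1 says a weighted analysis "to account for the randomised withdrawal design may also be presented", while Table 24 lists it with no such qualifier.

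**Schedule.** The laboratory markers are taken at Day 1 "and at Week 26, Week 52, Week 104, and (if applicable) at the ETD, Rescue and non-treatment follow-up visits" (SAP 3.4.9). In the Protocol 5.1 short-term schedule the later column is "Wk 26/ETD (early discontinuation of IP)/Rescue".

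**The concern.** The objective asks about add-on treatment for up to 52 weeks. By Week 52 the placebo column of an original-arm table holds some children who have taken active drug without metformin for 12 or 20 scheduled weeks. Each drug column holds some children who are no longer on add-on treatment. The SAP recognises this problem and defines a weighted correction for it. It applies the same weights to the continuous Week 52 outcomes HbA1c and FPG (SAP 4.6.2), but specifies none for continuous growth and bone outcomes. At stake is whether the Week 52 growth and bone tables answer the add-on question in a growing population.

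**Working it through.** **Plan's own figures.** 243 randomised over three arms gives 243 / 3 = 81 per arm. The stated power of about 80% (difference 0.75, SD 1.7, two-sided 0.05) reproduces at 80.2%. It concerns HbA1c at Week 26 and does not bear on this point.

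**Inputs.** n = 81 per arm (SAP 1.2); 1:1:1 and 1:1 allocation (SAP 1.2); W3 weights (SAP 4.7). The share r of an arm that is re-randomised is *not given*. I assume 0.10 to 0.40. It may differ between arms, in which case each formula applies with that arm's own r.

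**Does W3 do what is needed?** Weighted arm totals:
- drug: 0 × rn/2 + 2 × rn/2 + 1 × (1 − r)n = n
- placebo: 0 × 2rn/3 + 3 × rn/3 + 1 × (1 − r)n = n

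Each arm returns to its full size. The re-randomised children who stayed on their add-on regimen stand in for those randomised away from it.

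**Without weights.** Placebo children switched = 2r/3, half of them to each drug. Drug-arm children off metformin = r/2.

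**Cost of weights.** Effective n = (Σw)² / Σw². For drug this is n² / (4 × rn/2 + (1 − r)n) = n/(1 + r). For placebo it is n² / (9 × rn/3 + (1 − r)n) = n/(1 + 2r). With equal variances the standard error of the difference is multiplied by √[((1 + r) + (1 + 2r))/2] = √(1 + 1.5r).

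| r (assumed) | Placebo switched | of 81 | Drug arm off metformin | of 81 | Effective n, drug / placebo | SE multiplied by |
|---|---|---|---|---|---|---|
| 0.10 | 6.7% | 5.4 | 5% | 4.0 | 73.6 / 67.5 | 1.07 |
| 0.20 | 13.3% | 10.8 | 10% | 8.1 | 67.5 / 57.9 | 1.14 |
| 0.30 | 20.0% | 16.2 | 15% | 12.2 | 62.3 / 50.6 | 1.20 |
| 0.40 | 26.7% | 21.6 | 20% | 16.2 | 57.9 / 45.0 | 1.26 |

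**Does another planned summary supply the Week 52 add-on contrast?**
- *Up to Week 32 (SAP 4.7).* The last scheduled laboratory marker value before Week 32 is Week 26. Weight and height have a Week 32 value. Neither gives a Week 52 result.
- *By treatment received (SAP 4.7).* The rule is worded for ST+LT safety analyses in general. Table 24 lists such a version for AEs, SAEs and marked laboratory abnormalities, not for these measures. It also removes a selected group from placebo (metformin only, HbA1c below 7.5%, not rescued) without up-weighting similar children who stayed.
- *Randomised Withdrawal Subjects Data Set.* This is a randomised comparison at Week 52, but of monotherapy with continued metformin within each original arm, which is the separate monotherapy objective.
- *First and last treatment (SAP 4.1.5, 8.13).* Specified for the Week 104 analyses. The last-treatment grouping has the same selection problem as grouping by treatment received.

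**The case against.** The strongest reply has five parts.

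1. *The mixed table is not the only plan.* A reader might infer that the original-arm table is the sole planned 52-week comparison. The documents do not support that: the treatment-received rule, the withdrawal-set summaries and the first/last-treatment grouping all exist. What remains is that none is a randomisation-preserving contrast of add-on drug with placebo at Week 52.
2. *The W3 list is open.* Section 4.7 introduces its parameters as a selection that includes three named types, and Protocol 8.4.3.2 also plans weighting only for selected parameters. So the SAP does not exclude these measures and does not depart from the protocol. But neither the specific sections nor Table 24 adds them, so nothing commits the sponsor to producing the tables.
3. *Markers are not confined to Weeks 26 and 52.* They are also taken at rescue and early-discontinuation visits. This is correct, but it supplies no scheduled arm comparison between Weeks 26 and 52.
4. *Direction.* A reader might infer that mixing must pull the arms together and hide a drug effect. The documents do not establish this. Switched placebo children also lose metformin, and drug-arm children who stop metformin on the low dose move to the high dose. The net effect on a growth or bone marker is unknown.
5. *Size and consequence.* The upper value of r has no source. Eligibility is narrow, children recruited before sites implemented the third amendment could decline (Protocol 3.1), and some passed Week 32 or 40 before approval (SAP 4.2). The summaries are descriptive, so no test or error rate changes, and Week 26 is untouched. All of this stands and limits how much weight the point can carry.

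**Conclusion.** The gap holds in a limited form. SAP 4.7.6, 4.7.7.3, 4.7.7.4 and Table 24 specify no W3-weighted ST+LT summary for weight, height and BMI, growth and maturation markers or bone biomarkers, and the SAP is inconsistent about Tanner stage. Their Week 52 original-arm summary therefore does not isolate add-on drug from placebo with background treatment kept. The mixed shares are exact in r (2r/3 and r/2), but the percentages rest on the assumed range. The documents support no statement about the direction of distortion or about a wrong conclusion on growth or bone safety. This is a cheap improvement to a descriptive safety analysis.

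**What to change.** - Add W3-weighted Week 52 change-from-baseline summaries for weight, height and BMI (including z-scores), growth and maturation markers and bone biomarkers to SAP 4.7.6, 4.7.7.3, 4.7.7.4 and Table 24, shown beside the original-arm summaries.
- In 4.7.7.1, change *may* to *will* for the weighted Tanner analysis, so that it agrees with Table 24.
- Reconcile the general treatment-received rule in 4.7 with Table 24: either list that version for these measures or limit the rule to the parameters intended.

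This needs SAP wording and some additional tables from data already collected, with no change to dosing, visits or conduct. The price is precision: at 81 per arm the effective size is about 74 drug / 68 placebo at r = 0.10 and 58 / 45 at r = 0.40. The unweighted table should therefore stay alongside, and the effective sizes should be reported.

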4.7.1 Adverse events

4.7.1.1 All adverse events

Adverse events will be summarised as number and percentage of subjects by treatment group experiencing at least one AE within a category. Where specified, the number of events and incidence rate will also be provided. No statistical test will be performed to compare AE rates between treatment groups.

Only treatment emergent AEs with onset up to the cut-off dates defined in [Table 8](#) will be included in AE summaries. All AEs (including pre-treatment events) will be listed. Where relevant, AE listings will also include the most recent treatment dose received on or prior to AE onset.

The primary analyses of AEs will include data regardless of rescue medication initiation. Additional sensitivity analyses for AEs will be restricted to data collected prior rescue medication initiation.

An overall AE summary will be provided for the ST, ST+LT and randomised withdrawal periods, presenting the number and percentage of subjects by treatment group reporting at least 1 AE (excluding hypoglycaemic and DKA events that are not reported as SAEs) for the categories presented below. Incidence rates (as described in [Section 3.4.1](#)) adjusted for exposure time for ST+LT period might also be reported (as appropriate). The summary will be provided for both primary and sensitivity analyses for all treated subjects:

- At least one AE,
- At least one hypoglycaemia event,
- At least one AE or hypoglycaemia event,
- At least one SAE,
- At least one hypoglycaemia SAE,

- At least one adjudicated DKA SAE,
- At least one AE leading to discontinuation of study medication,
- At least one SAE leading to discontinuation of study medication,
- At least one hypoglycaemia SAE leading to discontinuation of study medication,
- At least one adjudicated DKA SAE leading to discontinuation of study medication,
- Deaths,
- At least one related AE,
- At least one related SAE,
- At least one AEOSI.

This analysis will be repeated for the combined ST+LT period up to Week 32 and also by treatment group received at the time of AE onset.

A weighted analysis for the overall AE summary will also be provided based on the ST+LT period, to account for the randomised withdrawal design (see Section 4.7 for details), and will include all data regardless of rescue medication initiation.

In addition, the overall AE summary will be repeated for subgroups based on race, ethnicity, sex, age group (using randomisation strata), region, baseline antidiabetic treatment, baseline HbA1c and baseline BMI, using the categories defined in the Appendix (Table 19). This will be provided based on the ST+LT period and will include all data regardless of rescue medication initiation and prior to rescue medication initiation. The overall AE summary will also be presented for the subgroup of subjects on a stable baseline dose of metformin IR or XR (with or without insulin).

The number and percentage of subjects with at least one AE will be summarised by SOC, PT and treatment group. AEs will be sorted by decreasing frequency within each SOC and PT according to the overall active treatment group, and, where applicable, by high dose active treatment or active treatment with background medication. As appropriate the number of events will also be displayed.

All adverse events will be summarised by SOC and PT (including incidence rate presented for PTs for the ST+LT period), regardless of rescue medication initiation unless otherwise specified, for:

- The ST period and the combined ST+LT period (including incidence rate).
- The ST period and the combined ST+LT period (including incidence rate), prior to rescue medication initiation.
- The combined ST+LT period, up to Week 32.

- The combined ST+LT period, excluding subjects randomised to withdrawal from metformin. A weighted analysis will be conducted on the Treated Subjects Data Set using the original randomised group and presenting weighted proportions.
- The combined ST+LT period. AEs will be summarised by treatment group received at the time of AE onset. For placebo subjects re-randomised to switch to dapagliflozin (or saxagliptin), AEs will be analysed in the placebo group to the beginning of the randomised withdrawal period and in the dapagliflozin (or saxagliptin) group if the event onset occurs during the randomised withdrawal period. AEs will be presented as incidence rate adjusted for exposure, as described in Section 3.4.1.
- The randomised withdrawal period. AEs with a date of onset occurring after the withdrawal baseline will be summarised using the Randomised Withdrawal Subjects Data Set separately for the three treatment comparisons described in Section 4.1.5.

The following descriptive summaries will also be provided for the ST, ST+LT and randomised withdrawal period, regardless of rescue medication initiation, for:

- Any AE by SOC, PT and maximum intensity (mild, moderate, severe).
- Any AE related to study drug (not related, related [including AEs with missing relationship to study drug]) by SOC and PT.
- Any AE by SOC and PT for common PTs (defined as PTs reported by $\geq 5\%$ of the subjects in any treatment group within the period). Number of events (and incidence rate for the ST+LT period) will also be presented.
- Any non-serious AE by SOC and PT

Summaries of AEs by SOC and PT will be provided by treatment group for the ST, ST+LT and randomised withdrawal period, regardless of rescue medication initiation, for the following subgroups:

- Age group using the randomisation strata (≥ 10 and < 15 years, ≥ 15 and < 18 years)
- Sex (male, female)
- Race (white, non-white)
- Baseline antidiabetic treatment (metformin only, insulin only, combination of metformin and insulin)

with age, sex and baseline antidiabetic treatment category being defined based on randomisation strata.

The ST+LT period presentations for Any AE by SOC and PT and Any AE by SOC and PT for common PTs will also be presented for the subgroup of subjects on a stable baseline dose of metformin IR or XR (with or without insulin).

In addition, AEs not included in the ST+LT analysis period per [Table 8](#) and those AEs reported quarterly between Week 56 and Week 104 will also be summarised for the post-study visit at Week 104.

No formal comparisons are made between treatments. No formal statistical testing will be performed, only summary statistics are provided.

A listing of all reported AEs falling into the ST+LT period will be produced. A separate listing will be provided for all AEs during the study.

Adverse events of special interest

MedDRA preferred terms and their groupings will be used to identify AEOSIs (as specified in [Section 3.4.1](#)) and will be listed and documented in the Study Master File. The number and percentage of subjects experiencing any of the specified AEOSIs and the individual terms that constitute each AEOSI grouping will be presented by preferred term for the ST, ST+LT and randomised withdrawal periods. Incidence rates of AEOSIs will also be presented for PTs for the ST+LT period. A glossary of the preferred terms used to identify AEOSIs will be provided by AEOSI category, along with a flag identifying any preferred term searched for but not present in the study.

COVID-19 related adverse events

A glossary of preferred terms related to COVID-19 will be provided, along with a flag identifying any preferred term searched for but not present in the study.

